6.3. Measures to Minimize Bias: Randomization and Blinding

Open-label using central randomization via interactive response technology (IRT) (IVRS/IWRS) Applies to Cohorts A, B1, and B2	
This is an open-label study; however, the specific intervention to be taken by a participant will be assigned using an IVRS/IWRS. Potential bias will be reduced by the central randomization.
 
Before the study is initiated, the telephone number and call-in directions for the IVRS and/or the log in information & directions for the IWRS will be provided to each site.
 
The site will contact the IVRS/IWRS prior to the start of study treatment administration for each participant. Randomization (Cohort A) or registration (Cohorts B1 and B2) will occur via IRT within approximately 28 days of start of screening. Randomized or registered participants will be dosed within 3 days after randomization or registration.
 
The site will record the randomized intervention assignment on the applicable case report form, if required. Once a randomization number has been assigned it must not be re-assigned.

--	--

As this is an open label study, the sponsor may conduct unblinded reviews of the data during the course of the study for the purpose of data cleaning at the patient level.

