## 5. GENERAL METHODOLOGY AND CONVENTIONS

### 5.1. Hypotheses and Decision Rules

#### 5.1.1. Hypotheses and sample size determination

##### Cohort A

Approximately 999 participants (including a minimum of 250 participants with CIS) will be randomized in a 1:1:1 ratio to one of the 3 treatment arms (A, B, or C) with approximately 333 participants randomized to each treatment arm in Cohort A, stratified by the presence of CIS (yes vs no) and geography (US vs Western Europe and Canada vs ROW).

The primary objective will be tested at a significance level of 0.025 (1-sided) associated with  $H_{01}$  described below:

$$H_{01}: HR_{EFS(AvsC)} \geq 1 \text{ vs. } H_{11}: HR_{EFS(AvsC)} < 1$$

where  $HR_{EFS(AvsC)}$  is the hazard ratio (HR) for EFS for Arm A vs Arm C.

In addition, the following statistical hypotheses will be tested to address the key secondary objectives:

$$H_{02}: HR_{EFS(BvsC)} \geq 1 \text{ vs. } H_{12}: HR_{EFS(BvsC)} < 1$$

$$H_{03}: HR_{OS(AvsC)} \geq 1 \text{ vs. } H_{13}: HR_{OS(AvsC)} < 1$$

$$H_{04}: HR_{OS(BvsC)} \geq 1 \text{ vs. } H_{14}: HR_{OS(BvsC)} < 1$$

[figure not shown]
where  $HR_{EFS(BvsC)}$  is the HR for EFS for Arm B vs Arm C,  $HR_{OS(AvsC)}$  is the HR for OS for Arm A vs Arm C, and  $HR_{OS(BvsC)}$  is the HR for OS for Arm B vs Arm C.

A graphical approach with group sequential testing outlined in Bretz et al. (2009) will be used to strongly control the family-wise type I error rate at a 1-sided 0.025 level as shown in Figure 3. The initial 1-sided alpha allocated to  $H_{01}$  is 0.025. If  $H_{01}$  is statistically significant,  $H_{02}$  and  $H_{03}$  will be formally tested at initial 1-sided alpha of 0.023 and 0.002, respectively. If

$H_{02}$  is statistically significant, alpha recycling will be applied to evaluate  $H_{03}$  at 1-sided 0.025 level. If  $H_{03}$  is statistically significant, all the alpha will be recycled to formally test  $H_{04}$ . One interim analysis on the OS endpoint is planned at the time of the EFS primary analysis. A Haybittle-Peto  $\alpha$ -spending function will be used to determine the efficacy boundary.

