Based on Protocol Amendment 5, the IA2 will be removed, and the FA for EFS based on a calendar-based data cut-off date will be conducted. Randomization to Cohort A was completed on 16 November 2021 and the EFS FA data cut-off date will be set to allow for approximately 3 years of follow-up after last randomized participant. The treatment period was completed on 16 November 2023. Based on the observed pooled blinded data of EFS accrual rate, approximately 261 EFS events are expected to have occurred across all three arms. Assuming equal event rate across three arms, approximately 174 events for each two-arm comparison are expected by the EFS FA data cut-off date.

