**Figure 3. Testing Strategy**

The power for EFS is estimated based on the following assumptions:

- median EFS for participants receiving BCG (induction and maintenance) is 24 months.
- treatment with PF-06801591 in combination with BCG (induction and maintenance) or BCG (induction only) is expected to increase the median EFS to 34.8 months, corresponding to a HR of 0.69 under the exponential model assumption.
- 20% drop-out rate for EFS within each arm.
- non-uniform participant accrual over 22 months.

- follow-up of approximately 33 months after the last participant is randomized.

For the primary endpoint, if the true HR is 0.69, 174 EFS events in Arm A and Arm C combined will provide 68.7% power to detect a difference using a 1-sided log-rank test at a significance level of 0.025.

Based on PA5, the FA for OS will be performed at the end of the study, which is approximately 5 years after the last participant has been randomized in Cohort A. Approximately 150 OS events are expected to have occurred across the three study arms assuming equal event rate across three arms (approximately 100 OS events for each two-arm comparison) by the OS FA data cut-off date.

If the primary objective is met, a gatekeeping approach will be used to allow further testing of the key secondary endpoints of EFS for Arm B vs. Arm C, OS for Arm A vs Arm C, and OS for Arm B vs Arm C as shown in [Figure 3](#).

- For the key secondary endpoint of EFS for Arm B vs Arm C ( $H_{02}$ ), if the true HR is 0.69 under the alternative hypothesis, 174 EFS events will provide 67.4% power to detect a difference using a 1-sided log-rank test at a significance level of 0.023.
- If both  $H_{01}$  and  $H_{02}$  are rejected, 100 OS events for Arm A vs C will provide 96.3% power to detect a HR of 0.472 using a 1-sided log-rank test at the 0.025 significance level and a 2-look group sequential design with Haybittle-Peto  $\alpha$ -spending function to determine the efficacy boundary. The hazard ratio of 0.472 corresponds to an increase in the 5-year Kaplan-Meier rate for OS from 0.80^13 in Arm C to 0.90 in Arm A, under the exponential model assumption.

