### **5.2.1. Data handling after the cut-off date**

Data after the cut-off date may not undergo the cleaning process and will not be displayed in any listings or used for summary statistics, statistical analyses, or imputations.

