### 6.1. Primary Endpoint(s)

#### 6.1.1. Event-free survival as assessed by investigator (Cohort A only)

##### 6.1.1.1. Primary analysis (for Arm A vs Arm C)

Refer to [Section 2.2.1](#) for the primary estimand.

In this study, disease may be assessed through cytology, cystoscopy, biopsy, and imaging scans conducted at screening (required), every 12 weeks for 2 years following randomization, and every 24 weeks thereafter until first occurrence of progression of disease, recurrence of high-grade disease, or persistence of CIS (for participants with CIS at baseline) regardless of initiation of subsequent anti-cancer therapy.

EFS is defined as the time from randomization until progression of disease, recurrence of high-grade disease, persistence of CIS, or death due to any cause, whichever occurs first.

An event is as defined in Table 10. The censoring and event date options to be considered for the EFS analysis ([Section 2.2.1](#)) are presented in Table 11.

$$\text{EFS (months)} = [\text{date of event or censoring} - \text{date of randomization} + 1]/30.4375$$

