## **7. INTERIM ANALYSES (COHORT A ONLY)**

### **7.1. Introduction**

The goals of the interim analyses are to allow early stopping of treatment arm(s) for futility or efficacy.

Prior to protocol amendment 5, two interim (IA1(futility only) and IA2) and final (FA) analyses were planned for the primary endpoint of Cohort A. IA1 for EFS was conducted after 658 participants were randomized to Cohort A for all 3 arms combined. As IA1 was for futility only, no alpha was spent at IA1.

Based on protocol amendment 5, the IA2 will be removed, and the FA for EFS based on a calendar-based data cut-off date will be conducted. Randomization to Cohort A was completed on 16 November 2021 and the EFS FA data cut-off date will be set to allow for approximately 3 years of follow-up after last randomized participant.

The interim efficacy analysis of OS will be performed as described in Sections 5.1.1 and 5.1.2 using the methodology described in Section 6.2.2.2.

As this is an open-label randomized study, the treatment is unblinded on participant level. However, the aggregate/cumulative data summaries by treatment arm will be unavailable to the study team and the external investigators until the database snapshot for the primary analysis.

Unblinded results from the interim futility analysis for EFS will not be communicated to the Sponsor's clinical team or to any party involved in the study conduct (apart from the independent statistician and E-DMC members) until the E-DMC has determined that either (i) EFS analysis has crossed the pre-specified boundary for efficacy or (ii) the study needs to be terminated due to any cause, including futility or safety reasons. Further details will be described in the E-DMC charter.

At the time of final EFS analyses, all participants will continue to be followed for OS until the final OS analysis (approximately 5 years after the last participant is randomized).

Based on PA5, since EDMC review of interim efficacy data (IA2) is no longer applicable, the study team will be unblinded to aggregate/cumulative data summaries by treatment arm at the time of FA for EFS. No additional EDMC activities are foreseen after the FA for EFS.

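### Does the 33-month follow-up in the SAP's EFS power assumptions leave the cut-off for the primary analysis in doubt?

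*SAP*

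**What the plan says.** SAP 5.1.1 (Cohort A) replaces the event-driven final EFS analysis with a calendar-based one and says that "the EFS FA data cut-off date will be set to allow for approximately 3 years of follow-up after last randomized participant". The same rule stands in the protocol (Synopsis and 9.2.1) and elsewhere in the SAP (2, 5.1.2 and 7.1). About 261 EFS events over three arms, or 174 per comparison, are projected from pooled blinded data. No minimum event count is set.

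Later in SAP 5.1.1, below the testing-strategy figure, the power assumptions for EFS are listed: a control median of 24 months, an experimental median of 34.8 months, 20% drop-out, non-uniform accrual over 22 months, and "follow-up of approximately 33 months after the last participant is randomized". The result follows: "For the primary endpoint, if the true HR is 0.69, 174 EFS events in Arm A and Arm C combined will provide 68.7% power". For Arm B against Arm C the SAP gives 67.4% at 0.023.

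On use of the cut-off, SAP 5.2.1 says: "Data after the cut-off date may not undergo the cleaning process and will not be displayed in any listings or used for summary statistics". On access to results, SAP 7.1 says that "aggregate/cumulative data summaries by treatment arm will be unavailable to the study team and the external investigators until the database snapshot" for the primary analysis.

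**The concern.** With no event count behind it, the calendar cut-off alone decides which data enter the primary test. SAP 5.1.1 appears to give that cut-off two values, 33 months and 3 years, and no calendar day is written down. Disease is assessed "every 12 weeks for 2 years following randomization, and every 24 weeks thereafter until first occurrence of progression of disease", so by August 2024 every participant is on the 24-week schedule. If visits are evenly spread, about 92/168 = 55% of those still followed would have a scheduled assessment between the two dates.

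Two things would be at stake. The primary test could come out differently at the two dates. And in an open-label trial, where the protocol (6.3) says "the sponsor may conduct unblinded reviews of the data during the course of the study for the purpose of data cleaning at the patient level", a loosely stated cut-off could in principle be settled with some knowledge of the results.

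**Working it through.** **Inputs.** From SAP 5.1.1: hazard ratio 0.69; 174 events in Arms A and C; 1-sided levels 0.025 (A vs C) and 0.023 (B vs C); medians 24 and 34.8 months; 22-month accrual; 20% drop-out with no time base given; last randomization 16 November 2021. From Protocol 4.1.1: 333 participants per arm planned, 1056 randomized in total, so 666 planned or 704 actual in two arms.

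**1. Reproduce the stated power.** Schoenfeld's formula with 1:1 allocation is power = Φ(√(D/4) × |ln HR| − z).

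- √(174/4) × |ln 0.69| = 2.447.
- At 0.025: Φ(2.447 − 1.960) = 0.687, the stated 68.7%.
- At 0.023: Φ(2.447 − 1.995) = 0.674, the stated 67.4%.

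Both match. Neither accrual, drop-out nor follow-up length appears in the formula.

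**2. Ask whether the 33 months produced the 174.** For exponential event hazard λ = ln 2/median and drop-out hazard η, a participant followed for time f has an event with probability λ/(λ+η) × (1 − exp(−(λ+η)f)). I averaged this over uniform accrual (an assumption, since the SAP says only that accrual was non-uniform), with f running from 33 to 55 months.

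| Reading of 20% drop-out | 666 in two arms | 704 in two arms |
|---|---|---|
| 20% by month 12 | 316 | 334 |
| 20% by month 33 | 383 | 405 |
| 20% by month 55 | 401 | 424 |

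All readings are far above 174. Replacing 33 by 36 months moves the list further away: the smallest of these figures rises from 316 to 323. So the 174 did not come from this list under either length. It is the blinded projection: 261 × 2/3 = 174.

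**3. Compare the cut-off statements.** The Synopsis and 9.2.1 of the protocol, and SAP 2, 5.1.1, 5.1.2 and 7.1, all give about 3 years after last randomization. The 33 months occurs once, as a power assumption. August 2024 is named nowhere as a cut-off.

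**4. Size if the primary test were run at both dates.** Calibrating a constant hazard to 261 events among 1056 participants at 3 years, with assumed drop-out from none to 50% and three accrual shapes, gives 163.5 to 173 events in Arms A and C at 33 months.

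- Power at 33 months: Φ(2.372 − 1.960) = 0.660 for 163.5 events; Φ(2.440 − 1.960) = 0.6845 for 173 events; against 0.687 for 174.
- Probability that the two tests disagree at HR 0.69, taking the two Z statistics as bivariate normal with correlation √(D33/174): 7.5% for 163.5 events, 5.5% for 168, 2.2% for 173.
- Probability at HR 1 that at least one is significant: 3.1% for 163.5 events, 2.7% for 173, against 2.5%.

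A single event, 173 against 174, already produces 2.2% disagreement. These percentages mostly reflect how close a test with about 69% power sits to its threshold. They also compare the planned analysis with one that nobody plans.

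**The case for a change.** The strongest case for a change is that a calendar trigger should be a date. The current SAP (version 8, 10 December 2024) is later than both derived dates and still speaks of the cut-off as something to be set. The same cut-off fixes the OS interim analysis. Treatment is known for each participant, and a recorded day is the most direct evidence that the cut-off did not depend on results. The SAP also says that the power was estimated from the listed assumptions, and a reader cannot recover 174 from them.

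The points about presentation stand: the 33-month item is out of date, the list does not explain the 174, and an exact day would be tidier. The point about independence from results is largely answered in the documents. The 3-year rule is anchored to a fixed past date. It was set in Amendment 5, dated 17 June 2024, before either derived date, with slow pooled event accrual as the reason (SAP 2). Arm-level summaries are withheld until the snapshot (SAP 7.1), and the access in Protocol 6.3 is for patient-level data cleaning. The 2.7% to 3.1% error rate requires choosing between two dates after seeing both results, and nothing in the documents suggests this. A sensitivity run at August 2024 would test a date that no document uses.

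**Conclusion.** No change to the plan is needed. The mismatch is a clerical leftover in the power assumptions, and the missing calendar day is detail that analysts can fill from a consistent rule: about 3 years from 16 November 2021. Correcting the item would leave 174 events, 68.7%, 67.4%, the significance levels and the test as they are. Even if the data were cut at 33 months, power at HR 0.69 would be 66.0% to 68.5% instead of 68.7%, under a constant hazard and the assumed range of drop-out and accrual; the documents do not give the number of events between the two dates. The conclusion rests on reading the six consistent cut-off statements as the rule and the single 33-month item as an assumption, which is how each is worded. The removed title pages could not be checked for a date.

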#### Cohorts B1 and B2

There will be no formal hypothesis testing for Cohorts B1 and B2.

Approximately 110 participants with BCG-unresponsive CIS will be enrolled in Cohort B1; this takes into account 10% of participants not meeting eligibility criteria. This sample size will allow for a 95% CI width for the CR rate to not exceed 0.21. The CR rate will be estimated in BCG-unresponsive CIS participants treated with PF-06801591.

[Table 8](#) provides exact 95% CIs for CR rate based on different possible observed responses in the BCG unresponsive CIS Cohort (Cohort B1).

**Table 8. Exact 95% Confidence Interval for CR rate**

Number of participants	Number of observed CRs	Observed CR rate	95% CI for True CR Rate
100	20	20%	(12.67%, 29.18%)
	25	25%	(16.88%, 34.66%)
	30	30%	(21.24%, 39.98%)
	35	35%	(25.73%, 45.18%)
	40	40%	(30.33%, 50.28%)
	45	45%	(35.03%, 55.27%)
	50	50%	(39.83%, 60.17%)
	55	55%	(44.73%, 64.97%)
	60	60%	(49.72%, 69.67%)

As of 31 August 2022, enrollment in Cohorts B1 and B2 was closed by the sponsor for business strategy reasons. This decision was not made due to any safety concerns, new emerging data, or regulatory interaction.

Due to the decision to close enrollment in Cohorts B1 and B2, the sample size for Cohorts B1 and B2 will not be achieved and the Cohort B1 and B2 objectives are no longer required.

### **5.1.2. Decision rules (Cohort A only)**

Prior to protocol amendment 5, two interim (IA1(futility only) and IA2) and final (FA) analyses were planned for the primary endpoint of Cohort A.

IA1 for EFS was conducted after 658 participants were randomized to Cohort A for all 3 arms combined. As IA1 was for futility only, no alpha was spent at IA1.

Based on protocol amendment 5, the IA2 will be removed, and the FA for EFS based on a calendar-based data cut-off date will be conducted. Randomization to Cohort A was completed on 16 November 2021 and the EFS FA data cut-off date will be set to allow for approximately 3 years of follow-up after last randomized participant.

Cohort A of the study will be considered positive if the primary objective is met.

One interim and one final efficacy analyses are planned for OS endpoints. The IA for OS will be performed at the time of the final analysis for EFS. The FA for OS will be performed at the end of the study, which is approximately 5 years after the last participant has been randomized in Cohort A:

- IA: at the time of the final analysis for EFS; approximately 64 OS events (64% of the 100 OS events expected for each comparison) are expected to have occurred for each comparison.
- FA: this will occur at the end of the study, approximately 5 years after last participant randomized; approximately 100 OS events are expected to have occurred for each comparison.

**Table 9. OS- Efficacy Boundaries**

OS Comparison	Arm A vs Arm C		Arm B vs Arm C	
Analysis	IA	Final Analysis	IA	Final Analysis
Analysis cutoff trigger	EFS final analysis	5 years after last participant randomized	EFS final analysis	5 years after last participant randomized
Number of events (information fraction) a	64 (64%)	100 (100%)	64 (64%)	100 (100%)
p-value (z-value) for efficacy if H01 is rejected but H02 is not rejected	<0.0001 (<-3.719 )	<0.00197 (<-2.883 )	<0.0001 (<-3.719 )	<0.00197 (<-2.883 )
p-value (z-value) for efficacy if both H01 and H02 are rejected	<0.0001 (<-3.719 )	<0.025 (<-1.96 )	<0.0001 (<-3.719 )	<0.025 (<-1.96 )

a. For IA, the number of events is that expected under the alternative hypotheses (for EFS and OS) at the time of final EFS analysis; for FA, the number of events is that expected under the alternative hypothesis for OS at 5 years after last participant randomized.

The efficacy boundary for OS will be updated based on the actual number of observed OS events for each comparison using the pre-specified  $\alpha$ -spending function. Therefore, the observed Z-test statistic at the IA for OS will be compared with the updated efficacy boundary. If OS is not met at the IA, the study for Cohort A will continue to the final analyses of OS, and the p-value that will be used to declare statistical significance at the FA for each comparison of OS will be based on the actual number of events documented at the cut-off date for the FA and the  $\alpha$  already spent at the IA. Further details are provided in [Section 7](#).

## 5.2. General Methods

As described in [Section 3.4](#), in this study ‘treatment arm’ or ‘cohort’ refers to one of the following:

### BCG Naïve Cohort (Cohort A)

- Arm A: PF-06801591 + BCG (induction and maintenance period)
- Arm B: PF-06801591 + BCG (induction period only)
- Arm C: BCG only (induction and maintenance period)

### BCG-Unresponsive Cohort

- Cohort B1: CIS with or without papillary disease: PF-06801591 only
- Cohort B2: Papillary disease only: PF-06801591 only

Endpoints will be summarized based on the analysis sets described in [Table 6](#) by treatment arm in Cohort A and for Cohort B1 and Cohort B2, unless otherwise specified.

### **5.2.1. Data handling after the cut-off date**

Data after the cut-off date may not undergo the cleaning process and will not be displayed in any listings or used for summary statistics, statistical analyses, or imputations.

### **5.2.2. Pooling of centers**

In order to provide overall estimates of treatment effects, data will be pooled across centers. The 'center' factor will not be considered in statistical models or for subgroup analyses due to the high number of participating centers in contrast to the anticipated small number of participants randomized/enrolled at each center.

### **5.2.3. Presentation of continuous and qualitative variables**

Continuous variables will be summarized using descriptive statistics i.e., number of non-missing values and number of missing values [i.e., n (missing)], mean, median, standard deviation (SD), minimum, maximum and first and third quartile (Q1 and Q3).

Qualitative variables will be summarized by frequency counts and percentages. Unless otherwise specified, the calculation of proportions will include the missing category. Therefore, counts of missing observations will be included in the denominator and presented as a separate category.

In case the analysis refers only to certain visits, percentages will be based on the number of participants still present at that visit, unless otherwise specified.

### **5.2.4. Definition of study day**

Start day of study treatment is the day of the first dose of study treatment.

The study day for assessments occurring on or after the start of study treatment (e.g., adverse event onset, tumor measurement) will be calculated as:

Study day = Date of the assessment/event – start of study treatment + 1.

The study day for assessments occurring prior to the first dose of study treatment (e.g., baseline characteristics, medical history) will be negative and calculated as:

Study day = Date of the assessment/event – start of study treatment.

The study day will be displayed in all relevant data listings.

